2. HIPOTHESIS AND OBJECTIVES

2.1 Hipotesis

The intake of bread produced following traditional breadmaking techniques is beneficial for people with quiescent Ulcerative Colitis (UC), but who present symptoms compatible with Irritable Bowel Syndrome (IBS), through the modulation of its intestinal microbiota.

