2.2 Objectius

To compare in vivo the influence of 2 types of bread, one long-fermented and one short-fermented, on the clinic and intestinal microbiota of patients with quiescent Ulcerative Colitis (UC), with symptoms compatible with IBS (Rome IV Criteria).

Specific objectives:

- To determine changes in the overall gut microbiota composition in patients with quiescent UC, before (V0) and after 8 weeks (VF) of the intake of traditional bread.
- To determine the correlation between the changes observed in the composition of the intestinal microbiota in V0 and VF and the clinical condition of the patient with quiescent UC.
- Assess the impact of traditional bread versus modern bread on improving the clinical response of patients with quiescent UC.

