3.2. Inclusion criteria

- > 18 years of age
- Patients diagnosed with ulcerative colitis according to established clinical and histological criteria as common clinical practice
- Remission of ulcerative colitis defined as a total Mayo score ≤ 2 and faecal calprotectin values under 250 ng/g
- Moderate-to-severe IBS-like symptomatology defined by Rome IV criteria and IBS Symptom Severity Score (IBS-SSS) > 175

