3.5. Randomization

Participants will be assigned to one of the two interventions using a random sequence separated by sex. It will remain double-blind throughout the study. In the case of withdrawal or abandonment of a participant, the new subject will be assigned a consecutive number and the intervention he will receive will be assigned using the same random sequence separated by sex as the rest of the participants.

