3.9. Statistical analysis

All statistical analyses will be performed using R software (2.14.0, <http://www.r-project.org/>). Pearson's chi-squared test will be used to determine whether there is a statistically significant difference between demographics and questionnaire data with more than one category. Normality for numerical data will be assessed through the Shapiro-Wilk test. For data with normal distribution, a paired t-test will be used to determine whether there is a statistically significant difference, whereas, for data with non-normal distribution, the Wilcoxon signed-rank exact test will be used. Significance levels will be established for $p \leq 0.05$.

Alpha diversity indices together with beta-diversity matrices will be computed by groups of intervention. Normality will be assessed through the Shapiro-Wilk test, and statistical differences in each treatment group will be analysed using Welch two sample t-test or paired t-test for data with normal distribution and Wilcoxon rank sum exact test or Exact Wilcoxon Signed-Rank test for data with non-normal distribution. For beta diversity matrices, unweighted Unifrac, weighted Unifrac and Bray-Curtis distances will be computed and plotted through principal coordinate analyses (PCoA).

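### Section 3.9 names no between-arm test for numerical clinical and laboratory outcomes, so objective 3 (traditional versus modern bread) goes untested on them

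*Combined protocol and SAP*

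**What the plan says.** The trial is randomised and double-blind (3.1), with two parallel arms of 48 patients (3.7). Allocation is stratified: "Participants will be assigned to one of the two interventions using a random sequence separated by sex" (3.5).

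Section 2.2 lists three specific objectives. The first concerns change in the microbiota from V0 to week 8 on traditional bread. The third is comparative: "Assess the impact of traditional bread versus modern bread on improving the clinical response of patients with quiescent UC". Section 2.1 claims benefit for these patients, "through the modulation of its intestinal microbiota", but ties the claim to no particular outcome.

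Section 3.9 provides these tests:

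- **Numerical data (first paragraph):** if normal, "a paired t-test will be used to determine whether there is a statistically significant difference"; if not, the Wilcoxon signed-rank test. Both are paired.
- **Demographics and categorical questionnaire data:** Pearson's chi-squared, without saying which groups are compared.
- **Diversity indices (second paragraph):** "statistical differences in each treatment group will be analysed using" Welch or paired t-tests, or the rank-sum or signed-rank test. This is the only place where two-sample tests are named.
- **Threshold:** "Significance levels will be established for" p ≤ 0.05. No adjustment, testing order or primary outcome is given there or elsewhere in the supplied text.

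**The concern.** Objective 3 asks whether one bread does better than the other. Patients are randomised individually to separate arms, so the only natural pair is the same patient at V0 and at week 8. A paired test then measures change within an arm and makes no use of the control arm.

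That matters because both arms may well improve together. Entry requires "IBS Symptom Severity Score (IBS-SSS) > 175" (3.2), and selecting on a high score can by itself produce a fall at week 8 through regression to the mean. Expectation and natural course can add to it. An analyst who follows 3.9 literally could report a significant improvement on traditional bread without having compared the breads on IBS-SSS, HADS, Mayo or any laboratory value.

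A second, lesser issue is that no single outcome is named to carry the claim of benefit, so any of several tests at 0.05 might be used for it.

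**Working it through.** **Inputs.** From the documents: 48 per arm (3.7), threshold 0.05 and paired tests (3.9). Assumed, because the documents do not give them: two-sided testing, the size of the common change, the correlation between V0 and week 8, and the number of outcomes that could carry the claim. The total of 96 cannot be reproduced, since the supplied text gives no effect size, SD or power for it.

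**1. Paired test in the traditional arm when both arms change equally.** Let d be the mean change divided by the SD of the change. The test statistic is noncentral t with 47 degrees of freedom and noncentrality d√48. For d = 0.2 / 0.3 / 0.5 the noncentrality is 1.39 / 2.08 / 3.46, and the chance p of a significant improvement is 0.273 / 0.530 / 0.924.

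**2. Traditional arm significant, modern arm not.** The arms are independent with the same p, so the chance is p(1 − p):

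| d | p | p(1 − p) | both significant, p² |
|---|---|---|---|
| 0.2 | 0.273 | 0.273 × 0.727 = 0.20 | 0.07 |
| 0.3 | 0.530 | 0.530 × 0.470 = 0.25 | 0.28 |
| 0.5 | 0.924 | 0.924 × 0.076 = 0.07 | 0.85 |

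**3. Between-arm test on the same data.** In 20,000 simulated trials per scenario (48 per arm, correlation 0.5, equal change in both arms), a comparison adjusted for baseline was significant in about 5% overall. It favoured traditional bread in 2.3% to 2.6%, whatever the size of the common change.

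**4. No deciding outcome.** Assume no true change and five outcomes, each able to carry the claim: Mayo, IBS-SSS, HADS, C-reactive protein and calprotectin. If they are independent, the chance of at least one favourable significant result in the traditional arm is 1 − 0.975⁵ = 0.119. With equal correlation it is 0.091 at 0.5 and about 0.06 at 0.8. One test gives 0.025. The family size drives the result: over correlations of 0.5 to 0, two outcomes give 4.5–4.9% and ten give 14–22%.

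**5. Detectable effects at 80% power (normal approximation, 96 patients analysed).** With r the correlation between V0 and week 8, in units of the score SD:

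- between arms, adjusted: 2.80 × √(2/48) × √(1 − r²)
- paired, one arm: 2.80/√48 × √(2(1 − r))

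| r | between arms | paired |
|---|---|---|
| 0.3 | 0.55 | 0.48 |
| 0.5 | 0.50 | 0.40 |
| 0.7 | 0.41 | 0.31 |

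**The case against.** Several points on the other side have weight.

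- **Paired tests are not wrong in themselves.** Objective 1 is a before/after question on traditional bread, and they suit it. This stands; the gap concerns objective 3.
- **Objective 3 is not wholly untested.** A reader might infer that no clinical comparison of the breads is planned. The documents do not support that. In 3.7 the Likert rating of improvement is among the questionnaires of the final visit but not of the baseline visit, so it cannot be paired. If treated as categorical, chi-squared could compare the arms on it. The gap is in the numerical scores and laboratory values.
- **The 27% / 53% / 92% in step 1 is not an error rate for objective 3.** It is the chance of detecting a change that is real by assumption. It bears on the loose claim of benefit in 2.1. It would be an error rate for superiority only if significance in one arm were read as superiority even when the other arm is significant too, and 3.9 states no such rule. The 20% / 25% / 7% in step 2 is closer to objective 3.
- **The pairs are not named.** That they are V0 and week 8 is an inference, though the design offers no other pairing.
- **A primary outcome may have been stated in text that was removed.** The reference list includes power-analysis sources that the visible text does not cite, so a calculation may have existed. The absence of a deciding outcome can therefore be asserted only for the supplied text. A primary outcome named elsewhere would still not put a between-arm test into 3.9.
- **Regression is not the only cure.** Welch or rank-sum, already named in 3.9, applied to the change scores would also compare the breads. Baseline adjustment is preferred for precision.

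**Conclusion.** The concern holds in this form: for numerical clinical and laboratory outcomes, 3.9 specifies within-patient tests only, and these do not answer objective 3. If both breads produce the same change of 0.2 / 0.3 / 0.5 SD, reading significance in one arm but not the other as a difference would wrongly favour traditional bread 20% / 25% / 7% of the time, against about 2.5% for a between-arm test. These figures assume 48 analysed per arm, two-sided 0.05 and the stated changes.

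The lack of a deciding outcome is secondary. Under an assumed family of five it raises the chance of a favourable false result from 2.5% to about 6–12% (correlations 0.8 to 0). Adjusting for multiplicity would not repair the missing comparison: with Bonferroni over five outcomes, the paired test in the traditional arm is still significant 11% / 28% / 78% of the time under the same equal changes.

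Confidence is high on what 3.9 says about numerical data, and lower on whether a primary outcome was ever stated. A reader might go further and conclude that 96 is the wrong sample size. The documents do not support that, because the supplied text gives no basis on which to confirm or refute it. The plan should be changed.

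**What to change.** Before unblinding, add to 3.9 for objective 3:

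> Primary analysis: difference between arms in total IBS-SSS at week 8 (or another single outcome the sponsor confirms), by linear regression adjusted for the V0 value and sex, two-sided 0.05. The claim that traditional bread is better than modern bread rests on this test. Other numerical outcomes are compared between arms with the same model and reported as secondary with 95% confidence intervals. Paired within-arm tests are kept for objective 1 and are not used as evidence that one bread is better than the other.

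IBS-SSS is a candidate because it defines eligibility and is recorded at both visits; the sponsor must make the choice. Sex enters the model because the random sequence is separated by sex.

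The cost is a change of method for the comparative question, not only of wording. No new data are needed, but the between-arm test is harder to win: with 96 patients and 80% power it detects about 0.55 / 0.50 / 0.41 SD at correlations of 0.3 / 0.5 / 0.7, against 0.48 / 0.40 / 0.31 SD for a paired test in one arm. Secondary results will carry less weight. Recruitment is charted for 2020; if unblinded data have already been seen, the choice must be reported as post hoc.

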3.6. Variables

a) Demographic variables

- **Age** expressed in years (y)
- **Sex** Male (M)/ Female (F)
- **Weight** expressed in IMC
- **Ethnic**: Caucasian/ African/ Asiatic/ American
- **Tobacco**: YES / NO / EX-Smoker
- **Age of UC diagnosis** expressed in years (y)
- **Familiar Antecedents** (YES/NO) which kind of disease?

b) Clinical variables:

- **Mayo Clinical Score** (*Clinical colitis activity index*) (Schroeder KW *et al.*

NEngl J Med 1987; 317: 1625-9). Punctuation range: 0-9 punts.

- **Rome IV Criteria** (Lacy BE, Mearin F, Chang L, *et al.* Bowel disorders. *Gastroenterology* 2016;150:1393-407).

- **IBS- SSS** (*Irritable Bowel Syndrome – Symptom Severity Score*) (Almansa C *et al.* *Rev Esp Enferm Dig* 2011 Dec;103 (12):612-8.

- **HADS** (*Hospital Anxiety and Depression Scale*) (Johnston M, *et al.* *J Psychosom Res* 2000;48:579-84.9)

- **Escala de Likert**: Subjective valuation of improvement of symptoms after the intervention

- **Adherence to Mediterranean Diet Questionnaire** (Estruch R *et al* *NEJM* 2013).

c) Analytical parameters:

Haemoglobin: blood haemoglobin concentration (g/dl).

Albumin: blood albumin concentration (g/dl).

Triglycerides: blood triglycerides concentration (mg/dl).

Cholesterol: blood cholesterol concentration (mg/dl).

C-reactive protein: blood C-reactive protein concentration (mg/dl).

Faecal calprotectin: faecal calprotectin concentration (µg/g).

d) Variables Microbiològiques

The microbiological profile of the microbiota of these patients will be analysed through high-throughput sequencing before and after the intervention.

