3.7. Methods

The proposed study will include 96 patients with UC in remission (Mayo Index ≤ 2 and Calprotectin ≤ 250 µg/gr), over 18 years of age, who have signed informed consent, who meet Rome IV criteria and present a moderate-severe severity index will be included (IBS-SSS >175). These patients will be randomized to one of the two intervention arms (N=48 per group):

- Treatment group: traditional bread (200g daily).
- Control group: modern bread (200g daily).

For both intervention groups stool and blood samples will be collected before starting the intervention (Visit 0 - Basal), and then after 8 weeks (Final Visit). The monitoring period will be 8 weeks. In addition, we will collect demographic data (age, sex, smoking habit, etc.), clinical data (Mayo index, Rome IV, IBS-SSS, CVE 20, HADS, PCR Likert scale, VSG, albumin, hemoglobin, faecal calprotectin, etc.), and microbiological variables.

The intervention will last 8 weeks and the following visits will be made during the study:

1. Consent- Pre-Randomization Visit

The patient will be evaluated by a doctor from the Gastroenterology service at the University Hospital [name] who will explain the study and evaluate the inclusion and exclusion criteria. Participants will be able to ask all the questions they have about it before signing the written consent. If the potential volunteer wishes to participate, after reading the informative documentation and receiving the relevant explanations, he must carefully read the informed consent and if he agrees with it he must sign it.

The patient will be provided with the 2 containers necessary to collect the stool sample at home for the following visits

2. Baseline Visit (V₀)

The patient will come to the visit with the stool sample corresponding to the basal Visit (V₀) before the intervention.

The demographic variables (age, sex, weight, ethnicity, smoking habit, family history, etc.) will be collected, the different established questionnaires and indexes will be completed (Rome IV, Mayo, IBS-SSS, CVE-20, HADS), and a blood test will be performed (PCR, Calprotectin, blood count, etc.).

The patient will be randomized and the bread will be provided according to the randomization result to intervention A or B. The patient will be told that he can collect the following portions of bread at the centre 1 or 2 times a week, for the next 8 weeks of intervention.

3. End of study Visit (EOS; W8)

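### Section 3.9 does not say which test serves which contrast for alpha diversity, or what is compared between arms, and names no arm comparison adjusted for V0

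*Combined protocol and SAP*

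**What the plan says.** Section 3.7 (Methods) sets the design: "The proposed study will include 96 patients with UC in remission", split equally with 48 per arm, and "For both intervention groups stool and blood samples will be collected before starting the intervention (Visit 0 - Basal), and then after 8 weeks (Final Visit". Section 3.6 (Variables) adds that the microbiota will be "analysed through high-throughput sequencing before and after the intervention". Each patient who completes both visits therefore has a V0 and a VF value for every alpha-diversity index.

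Section 3.9 (Statistical analysis) has one sentence on testing these indices. After a Shapiro-Wilk check, "statistical differences in each treatment group will be analysed using Welch two sample t-test or paired t-test for data with normal distribution". For indices that fail the check, the sentence offers the unpaired and the paired Wilcoxon test in the same either-or form. The threshold is p ≤ 0.05, with sidedness not stated. No regression or covariance model appears in the section.

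Section 2.2 (Objectives) needs two different contrasts. The general aim compares the two breads on symptoms and microbiota. The first specific objective concerns change from V0 to VF on traditional bread.

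**The concern.** Two contrasts are wanted (between arms, and V0 to VF within an arm) and two kinds of test are named (two-sample and paired), joined only by an 'or'. The normality check decides between t and Wilcoxon. It does not decide between paired and unpaired. Taken literally, the sentence attaches all four tests to differences inside each arm and defines no arm comparison of alpha diversity at all. That the two-sample tests are meant to compare arms has to be inferred from their names and from section 2.2.

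Even on that inference, the quantity compared is open. A two-sample test takes one number per patient, which could be the VF value or VF minus V0. The first makes no use of V0. The second subtracts V0 in full, whatever the actual correlation between visits. The usual more precise choice, V0 as covariate, is not named.

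At stake is the precision of the microbiota comparison between breads, together with a choice of analysis that is still open when the data are seen.

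**Working it through.** **Inputs from the documents.** 48 per arm and 96 in total (3.7; 2 × 48 = 96); significance level 0.05 (3.9); V0 and VF samples in both arms (3.6, 3.7).

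**Assumptions, not in the documents.** Two-sided testing; equal SD at V0 and VF, set to 1; no dropout; V0-VF correlation ρ of 0.3, 0.5 or 0.7; true arm difference of 0.5 SD. The text available gives no effect size, SD or power, so the figure of 96 cannot be reproduced beyond the sum above.

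**Effective SD per patient, s, for each arm comparison**

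- VF only: s = 1
- Change, VF − V0: s = √(2(1−ρ))
- V0 as covariate: s = √(1−ρ²)

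The covariate variance divided by the VF-only variance is 1−ρ². Divided by the change-score variance it is (1−ρ²)/(2(1−ρ)) = (1+ρ)/2. Both ratios are below 1 for any ρ strictly between 0 and 1, so V0 as covariate is the most precise of the three whichever of the other two was intended.

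**Power.** The standard error is s√(2/48) = 0.2041s, and power = Φ(0.5/(0.2041s) − 1.96).

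Example at ρ = 0.5 with V0 as covariate: s = √0.75 = 0.866; 0.5/(0.2041 × 0.866) = 2.83; Φ(2.83 − 1.96) = Φ(0.87) = 80.7%.

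| ρ | VF only | Change | V0 as covariate |
|---|---|---|---|
| 0.3 | 68.8% | 54.4% | 72.8% |
| 0.5 | 68.8% | 68.8% | 80.7% |
| 0.7 | 68.8% | 88.5% | 92.9% |

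A simulation of 5,000 trials per ρ, using Welch tests and a fitted covariate model, gave 68.7/54.1/72.7%, 66.9/67.1/79.1% and 67.1/87.3/91.4%. These lie within about two points of the formula.

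**Detectable difference at 80% power.** (1.96 + 0.84) × 0.2041 × s gives 0.572 SD for VF only. With V0 as covariate it is 0.546, 0.495 and 0.408 SD at ρ = 0.3, 0.5 and 0.7.

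**Equivalent sample size.** 48/(1−ρ²) = 52.7, 64.0 and 94.1 patients per arm analysed on VF only.

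**Change scores.** At ρ = 0.3 they do worse than VF only, at 0.5 the two are equal, and at 0.7 change scores do better. Settling the ambiguity in favour of change scores would therefore not be a safe repair.

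**The case against.** The strongest reply is that the sentence is loosely worded but its intent is plain: two-sample tests between arms, paired tests within arms. The first paragraph of 3.9 prescribes only paired tests for numerical data, so the authors had not overlooked pairing. Under randomisation, a Welch test on VF values or on changes is unbiased for the arm difference and keeps its nominal size; chance imbalance at V0 is already covered by the standard error. The text available does not name alpha diversity as the primary outcome or tie the sample size to it. The gain can also be small: four power points over VF only at ρ = 0.3, and about four over change scores at ρ = 0.7.

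Most of this stands. It makes the point one of precision and specification, not validity. It does not say which value is compared between arms, and it does not supply an adjusted analysis.

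A reader might infer two stronger things.

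- **That the arm comparison ignores each patient's V0 value.** The documents do not say so. A Welch test on VF minus V0 fits the wording and uses V0.
- **That an unpaired V0-versus-VF test is planned inside an arm.** Such a test would be badly conservative: with 48 patients its true size would be 1.9%, 0.6% or 0.03% at ρ = 0.3, 0.5 or 0.7. Its power for an assumed 0.4 SD change would be 50%, against 65%, 79% or 95% paired. The literal wording permits it, but paired tests stand in the same sentence and the division between arms and within arms is the more natural reading. These figures describe what the 'or' leaves possible, not what the plan has chosen.

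**Conclusion.** The point holds as a gap in specification and a likely loss of precision. Section 3.9 leaves open which test serves which contrast and what is compared between breads, and it names no V0-adjusted comparison although the data for one are already planned.

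For a true difference of 0.5 SD, adjusting for V0 gains about 4 to 24 power points over VF only (72.8 − 68.8 at ρ = 0.3; 92.9 − 68.8 at ρ = 0.7). Over change scores it gains about 18 to 4 points across the same range (72.8 − 54.4; 92.9 − 88.5). Direction and ranking follow from equal variances and a positive correlation below 1. The size rests on an assumed correlation and an assumed effect, neither of which the documents give.

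The documents do not support calling the arm comparison biased or invalid. The change should be made because it is cheap and removes an open choice.

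**What to change.** Replace the alpha-diversity testing sentence in 3.9 with wording such as:

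> For each alpha-diversity index the arms are compared by a linear model of the VF value on arm, the V0 value and sex (the factor separating the random sequence), reporting the adjusted difference with 95% CI. If residuals are clearly non-normal, the index is transformed or the same model is fitted to ranks. V0-VF change within an arm is described with paired tests only (paired t or signed-rank); two-sample tests are not used for V0 versus VF within an arm.

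Sex belongs in the model because section 3.5 (Randomization) keeps separate sequences for men and women. The provision for non-normal residuals takes over the role of the present Shapiro-Wilk and rank-sum route. It should be fixed in the plan before the data are unblinded, including whether transformation or ranks comes first.

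The cost is a change of wording and one regression per index. No extra sample, visit or sequencing is needed.

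### Section 3.9 states no valid test of microbiota composition: the UniFrac and Bray-Curtis distances are plotted but not tested, and no per-patient composition measure is defined

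*Combined protocol and SAP*

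**What the plan says.** Section 2.2 gives the general aim as "To compare in vivo the influence of 2 types of bread, one long-fermented and one short-fermented, on the clinic and intestinal microbiota". Its first specific objective is "To determine changes in the overall gut microbiota composition in patients with quiescent UC", comparing baseline (V0) with the final visit (VF) under traditional bread.

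The second paragraph of section 3.9 holds the whole microbiota analysis:

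- It opens by mentioning alpha indices and beta-diversity matrices together, both obtained by intervention group.
- After a normality check, it says "statistical differences in each treatment group will be analysed using Welch two sample t-test or paired t-test", with rank-sum or signed-rank tests for non-normal data.
- It then turns to the distances alone: "unweighted Unifrac, weighted Unifrac and Bray-Curtis distances will be computed and plotted through principal coordinate analyses (PCoA").

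Section 3.6 d) describes the microbiological variable in one sentence: "The microbiological profile of the microbiota of these patients will be analysed through high-throughput sequencing before and after the intervention". Section 3.8 covers storage, DNA extraction and sequencing, and gives no derived variable.

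**The concern.** A PCoA plot describes how samples lie relative to each other. It carries no error rate and does not say whether an apparent separation exceeds chance. If section 3.9 is followed as written, the trial can report alpha-diversity p-values and ordination plots. It cannot say, at a stated error rate, whether composition changed under traditional bread or changed differently under the two breads. The hypothesis in section 2.1 attributes the benefit to modulation of the microbiota, so this is a central question.

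An analyst who fills the gap later has to decide which distance leads and how the V0-VF pairing and the allocation enter the test. Those decisions are best made before the data are seen.

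**Working it through.** **Step 1: objectives against methods.** The plan states no figure on this point, so the check is textual.

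| Question (section 2.2) | What section 3.9 provides |
|---|---|
| V0-VF change in composition, traditional bread | Three distances, displayed by PCoA; no test linked to them |
| Bread versus bread, composition | The same |
| Bread versus bread, alpha diversity | Welch or rank-sum test arguably available, though the reference to each treatment group leaves this unclear |

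**Step 2: can the named tests be carried over to the distances?** Each needs one independent value per patient (or per patient and visit). With 48 patients per arm (section 3.7), a distance matrix for one arm at one visit holds 48 × 47 / 2 = 1,128 entries. Every patient appears in 47 of them, so they are not independent observations.

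Valid per-patient values could be derived, for example a PCoA axis score or each patient's own V0-VF distance. The plan names neither as a variable. A patient's own V0-VF distance could be compared between arms, but it would not by itself answer objective 1: it is never negative, so testing its mean against zero is uninformative.

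**Step 3: illustration.** From the documents: 48 per arm (section 3.7) and the 0.05 level (section 3.9). Section 3.5 foresees replacements ("In the case of withdrawal or abandonment of a participant, the new subject will be assigned a consecutive number"), so I took 48 complete pairs per arm. All else is assumed: 60 taxa, log-normal abundances with SD 1.5, 10,000 reads, between-person share of variance 0.5 or 0.7, a random tree for UniFrac, arms balanced by sex, 499 permutations. There were 3,000 runs per setting with no effect and 1,000 with drift. Drift means an equal shift in both arms of 0.25 or 0.35 SD in 9 of 60 taxa.

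| True situation | Test | Significant at 0.05 |
|---|---|---|
| No effect | Between-bread PERMANOVA, Bray-Curtis | 4.8% / 5.3% (share 0.5 / 0.7) |
| No effect | V0-VF PERMANOVA in traditional arm, each distance | 4.8-5.6% |
| No effect | Per-patient V0-VF distance compared between arms | 4.2-5.5% |
| No effect | Paired test on PCoA axis 1-2 scores | 4.2-5.4% |
| No effect | t or Wilcoxon on raw pairwise distances | 63-76% |
| No effect | Between-bread PERMANOVA, any of three distances, unadjusted | 12.0% / 13.6% |
| Equal drift in both arms | V0-VF in traditional arm, Bray-Curtis | 20-51% |
| Equal drift in both arms | Between-bread, Bray-Curtis | 4.9-5.1% |

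A simpler model (30 taxa, 500 runs, Bray-Curtis) gave 67% for a Welch test on raw pairwise distances, 5.4% for the same test on per-patient V0-VF distances, and 5.2% for PERMANOVA at VF.

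**Step 4: what a per-patient score could detect.** Assume two-sided 0.05 (sidedness is not stated) and 80% power. Between arms, the normal approximation is (1.960 + 0.842) × √(2/48) = 0.57 SD; the exact t calculation gives 0.58. For a paired change within one arm, 2.802 / √48 = 0.40 SD; exact 0.41.

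**The case against.** The strongest reply is that the plan contains more inference than a quick reading suggests, and much of that reply stands.

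- The t/Wilcoxon sentence directly follows one naming both alpha indices and beta-diversity matrices, and nothing restricts it to alpha diversity. A reader might infer that the tests are confined to alpha diversity; the text does not say so. It also does not say what value they would be applied to for beta diversity, and that is the gap.
- A reader might infer that the microbiota comparison between breads has no inferential answer at all. That goes too far. The general objective speaks of the microbiota, not only its composition, and a between-bread alpha-diversity test is arguably available. The generic tests for numerical data could also be run on taxon abundances, although no taxon is named and those tests are paired.
- PCoA yields axis scores, and in the illustration paired tests on them hold their level. What is missing is a statement that these scores will be tested.
- A reader might infer that distances and contrasts will all be picked after the results are seen. The three distances are named in section 3.9 and both contrasts follow from section 2.2. Only their hierarchy and the test are open.
- The simulated rates belong to tests that the plan does not name. Nothing in the documents says that raw pairwise distances will be tested or that any one significant distance will count, so 63-76% and 12-14% are not predictions for this trial.

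**Conclusion.** The point holds in a bounded form: no valid test of composition is stated, either for V0-VF change under traditional bread or for the composition part of the bread comparison. This rests on the wording of sections 2.2, 3.6, 3.8 and 3.9 and on the requirement of one independent value per patient. It needs none of the simulated figures.

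Those figures depend on assumed inputs and serve two limited purposes. They show why t or Wilcoxon tests should be kept off raw pairwise distances, and why a before-after change in one arm cannot be credited to the bread: under equal drift it was significant in 20-51% of runs while the between-bread test stayed near 5%.

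The gap should be closed before analysis. It does not undermine the sampling, the sequencing or the randomisation.

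A separate, minor point: the second specific objective, "To determine the correlation between the changes observed in the composition of the intestinal microbiota in V0 and VF and the clinical condition", also has no stated coefficient, composition measure, clinical measure or handling of arm. That is missing detail and is not part of the size of this finding.

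**What to change.** Add to section 3.9:

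1. **Lead distance.** Name one, for example Bray-Curtis, and label the other two supporting.
2. **Between-bread question.** Specify a PERMANOVA arm-by-visit test that permutes arm labels between whole patients within sex. This matches section 3.5: "Participants will be assigned to one of the two interventions using a random sequence separated by sex". Alternatively, pre-name a per-patient composition-change score and compare it between arms. The score must be chosen with care: a V0-VF distance captures how far a patient moved, whereas a change in axis score keeps direction.
3. **Objective 1.** Specify a PERMANOVA of V0 versus VF in the traditional-bread arm, permuting visit labels only within patient, with a dispersion check. State that a within-arm change alone cannot be attributed to the bread.
4. **Scope of t and Wilcoxon tests.** Limit them to alpha indices and other per-patient values, and exclude raw pairwise distances.

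The cost is a few lines of R on data already being generated, with no new samples or visits. The lead distance must be fixed in advance and may miss a shift that another distance would show. Between-bread power may be modest: under the assumed model, a shift of 0.25, 0.35 or 0.50 SD in the traditional arm alone gave 10-13%, 17-26% and 40-53% on Bray-Curtis. A non-significant result should therefore not be reported as evidence of no difference.
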